## 9.7.1.1 Calculation of Annualized Bleeding Rates (ABR)

The annualized bleeding rates (ABR) will be calculated as follows: (total number of bleeding episodes÷observed treatment period in days) \* 365.25.

The treatment period for emergency surgery will be excluded from the bleed rate calculation.

Bleeding occurring prior to the first prophylactic infusion will not be included for the estimation of bleed rate. The observation period for the on-demand regimen will commence on the day of enrollment (met all inclusion and exclusion criteria); the period for the prophylaxis arm will commence at the first prophylactic infusion once enrolled (met all inclusion and exclusion criteria).

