# 2. LIST OF ABBREVIATIONS AND GLOSSARY

Abbreviation	Definition
ABR	annualized bleed rate
ADL	Activity of Day Living
AE	adverse event
AICC	anti-inhibitor coagulant complex
APCC	activated prothrombin complex concentrates
aPTT	activated partial thromboplastin time
B19V	parvovirus B19
BPA	by-passing agent
BU	Bethesda unit
BW	body weight
CRF	case report form
Chronic pain	continuous and/or intermittent pain, related to the pathophysiology of haemophilia, requiring intervention (pharmacological or non-pharmacological treatment), and in which the cause of pain cannot be readily removed, occurring more than once a week and lasting 3 months or more 
DIC	disseminated intravascular coagulation
EC	ethics committee
ECG	electrocardiogram
eCRF	electronic case report form
ER	emergency room
ETP	endogenous thrombin potential
FEIBA	Factor Eight Inhibitor Bypassing Activity
FEIBA NF	Factor Eight Inhibitor Bypassing Activity Nanofiltered
FVIIa	activated factor VII
FVIII	factor VIII
FIX	factor IX
GPV	Global Pharmacovigilance
HAL	Haemophilia Activities List 
HAV	hepatitis A virus
HBV	hepatitis B virus
HCV	hepatitis C virus
HEV	hepatitis E virus
High responding inhibitors:	inhibitors with peak activity >5 Bethesda Units (BU/ml) at any time associated with anamnesis following replacement of the missing clotting factor 
HIV	human immunodeficiency virus
HJHS	Haemophilia Joint Health Score

Abbreviation	Definition	
HRQoL	Health-Related Quality of Life	
HRUR	health resource used related	
ICF	informed consent form	
IQR	inter quartile range	
ITI	immune tolerance induction	
MAH	marketing authorization holder	
MBR	monthly bleed rate	
MRI	magnetic resonance imaging	
NMC	non-medical complaint	
NRS	numerical rating scale	
NSAE	non-serious adverse event	
On-demand treatment	treatment of acute bleeds with any factor concentrates with the goal to resolve bleeds	
PD	pharmacodynamic(s)	
PedHAL	Pediatric Haemophilia Activity Level	
Prophylaxis	Regular administration of factor concentrates with the goal to prevent bleeds. For analysis purposes, in this protocol, prophylaxis is defined as follows:  • continuous prophylaxis (>46 weeks; long-term)  • intermittent prophylaxis (>12 weeks-46 weeks)  • episodic prophylaxis (≤12 weeks)  • peri-Immune Tolerance Induction (ITI) prophylaxis  For analysis purposes FEIBA prophylaxis is defined as at least three administrations per week 	
QoL	quality of life	
RoM	range of motion	

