# 9.1.2 Secondary Endpoints

#### 9.1.2.1 Joint Health/Function Outcomes

- Joint clinical outcomes in routine clinical practice setting, using any therapeutic regimen, assessed as in common practice, by:
  - ➤ WFH Orthopedic Joint Score (Gilbert scale) and Haemophilia Joint Health Score (HJHS)
  - > X-ray using Pettersson scale
  - Magnetic Resonance Imaging (MRI) and or ultrasound scanning
  - Number of total target joints (defined as 3 or more bleeds in the same joint in a 6-month period )
  - Number and reason of invasive surgical procedures, such as (but not exclusively) orthopedic surgery, radiosynovectomy and chemosynovectomy Number of breakthrough bleeding events in patients on prophylaxis and number of consecutive months on prophylaxis

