#### 9.3.3 Economic Variables

- Health resource use:
  - Number of visits at the site
  - > Unscheduled visits at the site
  - Number of hospitalizations and length of stay (number of days) related to haemophilia (surgery excluded)
  - Length of stay in hospital per inpatient hospitalization
  - Number of days lost from school or work due to bleeding episodes
  - ➤ Antiphlogistic drug use

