## 11.2.8 Untoward Medical Occurrences Not Considered Adverse Events

For the purposes of this study, each of the following events experienced after the Informed Consent signature will not be considered an AE, and thus, not included in the analysis of AEs:

- Non serious bleeding events that are considered due to the underlying disease by the investigator.
- Elective surgeries: Elective and planned surgeries, when these surgeries relate to a preexisting disease (see also Section 11.2.6) that has not worsened during study participation, will not be considered as (S)AEs

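### The bleed rate excludes only emergency-surgery time, so FEIBA NF cover for elective surgery stays in the primary ABR, and no surgical cover leaves the prevention dose table

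*Protocol*

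**What the plan says.** Section 9.7.1.1 computes the ABR as "total number of bleeding episodes÷observed treatment period in days", multiplied by 365.25. It then states: "The treatment period for emergency surgery will be excluded from the bleed rate calculation". This is the only surgical exclusion in the analysis of bleeding or dose, and it applies only to the bleed rate.

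The protocol expects elective procedures. Section 9.1.2.1 makes an endpoint of the "Number and reason of invasive surgical procedures, such as (but not exclusively) orthopedic surgery, radiosynovectomy and chemosynovectomy". Section 11.2.8 removes from adverse event reporting "Elective and planned surgeries, when these surgeries relate to a preexisting disease" that has not worsened. Section 9.3.3 leaves surgery out of the haemophilia hospitalisation count, so the protocol does separate surgery when it means to.

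On classification, the glossary describes prophylaxis as "Regular administration of factor concentrates with the goal to prevent bleeds". FEIBA prophylaxis requires at least three administrations a week, and the episodic class runs up to 12 weeks with no lower limit. Table 1 records FEIBA NF infusions under two purposes only, bleeding episodes and prophylaxis, and refers to the glossary. In 9.7.1.1, "the period for the prophylaxis arm will commence at the first prophylactic infusion once enrolled", and bleeding before that infusion is not counted.

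The dose table for prevention in 9.7.3.2 covers prophylaxis and on-demand subjects and mentions no surgical exclusion.

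**The concern.** ABR by regimen is the primary endpoint (9.7.3.1). It is meant to describe bleeding under routine on-demand treatment or routine prophylaxis. Peri-operative cover is given for a procedure and is neither. The protocol accepts this for emergency surgery but gives no reason why elective surgery differs.

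This is not a detail left to the statistical analysis plan. The protocol fixes the exclusion and its limit, so an analysis that follows it keeps elective cover in the rate. Two consequences are possible, and they are alternatives:

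- **Cover is not counted as prophylaxis.** The covered days stay in the on-demand denominator, or in the longer prophylaxis period already under way. Any post-operative bleed that is recorded as a bleeding episode stays in the numerator.
- **Cover is counted as prophylaxis.** Regular cover at least three times a week can fit the episodic class. The first covered infusion could then fix the start of the subject's prophylaxis period because of an operation.

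Under either reading, surgical consumption is mixed into the regimen dose summary.

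**Working it through.** The protocol gives no figure for the effect of this rule, so there is nothing to reproduce first. One input can be checked: the two ABRs cited in section 7.1 give (28.7 − 7.9)/28.7 = 72.5%, which matches the reduction stated there.

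**Inputs from the protocol**
- On-demand ABR 28.7 and prophylaxis ABR 7.9 (section 7.1)
- Observation of four years per subject (9.2.2), that is 4 × 365.25 = 1,461 days
- Minimum period for an ABR of 90 days (9.7.1.2, 9.7.3.1)
- Episodic prophylaxis of at most 12 weeks (glossary)

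**Assumptions**
- Cover of d = 14 to 42 days per operation; the protocol gives no duration
- Bleed rate under cover r = 0, with r = 7.9 per year as a sensitivity value

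**On-demand subject, cover kept in the period.** ABR = [28.7 × (T − d) + r × d]/T, where T is the observation time in days. With the cover excluded, the ABR stays at 28.7.

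| T | d = 14, r = 0 | d = 42, r = 0 | d = 14, r = 7.9 | d = 42, r = 7.9 |
|---|---|---|---|---|
| 1,461 days | 28.4 | 27.9 | 28.5 | 28.1 |
| 365.25 days | 27.6 | 25.4 | 27.9 | 26.3 |
| 90 days | 24.2 | 15.3 | 25.5 | 19.0 |

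For example, 28.7 × (1,461 − 42)/1,461 = 27.9 and 28.7 × (90 − 42)/90 = 15.3. With r = 0 the relative fall is 1 to 3% over four years, 4 to 12% over one year and 16 to 47% at 90 days.

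**Opposite direction.** Take a prophylaxis subject at 7.9 with a 42-day window containing k = 1 to 3 post-operative bleeds, and assume that these are recorded as bleeding episodes.
- One year: 7.9 × (365.25 − 42)/365.25 + k = 7.0 + k, giving 8.0 to 10.0.
- Four years: 7.9 × (1,461 − 42)/1,461 + k/4 = 7.67 + k/4, giving 7.9 to 8.4.

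**Can cover have its own ABR?** An episodic course lasts at most 12 × 7 = 84 days, which is below 90. A single course therefore yields no ABR of its own. It can still affect the start of the prophylaxis period and the dose table.

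**Which dose table is affected?** The bleed-treatment table in 9.7.3.2 is restricted to treated bleeds, so cover does not belong there. The prevention table has no such restriction. Because 9.7.1.1 concerns only the bleed rate, even emergency cover stays in it.

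**The case against.** The strongest counter-argument is size. Over the planned four years the ABR moves by 1 to 3% under the assumptions above, and the 15.3 figure needs 42 of only 90 days to be surgical cover. That stands. The dose tables report medians and quartiles, which resist a few operated subjects, and no document says how many elective operations to expect. Describing all FEIBA NF use is also legitimate in a routine-practice cohort. That supports reporting surgical use, but not merging it into the regimen figures.

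A second argument is that whether peri-operative cover counts as regular administration is an operational decision that an analysis plan can take. That is fair for the classification, which is why both branches are given. It does not answer the exclusion itself, which the protocol limits to emergency surgery.

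Three stronger readings are tempting, and the documents do not support them.

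- **One operation doubles a subject's annualised dose.** Assume 14 to 28 cover days at 100 to 200 U/kg per day, which is 1,400 to 5,600 U/kg. Spread over four years this adds 350 to 1,400 U/kg per year. An on-demand year at 28.7 bleeds × 1 to 2 infusions × 85 U/kg is about 2,440 to 4,880 U/kg. The addition is 350/4,880 = 7% to 1,400/2,440 = 57%. Doubling needs a period of about one year and a favourable pairing of extremes. Section 9.2.1 also gives 200 U/kg as a daily maximum rather than a guideline dose, and 1 to 2 infusions per bleed is the Excellent category of Table 3.
- **Cover both dilutes on-demand time and moves the subject to prophylaxis.** The same days cannot do both.
- **The distortion is non-random because surgery falls on subjects with the worst joints.** This may be plausible, but nothing in the documents establishes it.

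**Conclusion.** The point holds as a defect in a stated rule for the primary endpoint: elective-surgery cover stays in the ABR, and no surgical cover is taken out of the prevention dose summary. For a subject followed for the full four years the ABR effect is minor. It becomes material when the regimen period is short, as with early discontinuation or a change of regimen. The direction is not fixed, because bleed-free cover lowers the rate and post-operative bleeds raise it. With about 55 subjects divided by regimen and prophylaxis subtype, a few operated subjects with short periods could shift a subgroup summary.

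The sizes rest on assumed cover lengths and bleed rates under cover, and on a cited ABR from another study. The existence of the problem does not rest on them. Given how cheap the correction is, it should be made.

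**What to change.** In 9.7.1.1, replace the reference to emergency surgery with surgery, whether emergency or elective. Then:

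1. Define a peri-operative window from the surgical procedures and FEIBA NF infusions that Table 1 already collects, assuming that their dates are captured.
2. Remove the days and bleeds inside that window from the ABR numerator and denominator.
3. State that surgical cover neither starts nor defines a prophylaxis period, and reconcile this with the glossary.
4. In 9.7.3.2, report FEIBA NF use under surgical cover on its own line, apart from the regimen dose summaries. This also serves the secondary objective in 8.3 on use in different clinical settings.

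The cost is a small loss of observation time in operated subjects and somewhat more than a wording change. Table 1 distinguishes only bleeding and prophylaxis infusions, and the diary list in 9.4.2 names no reason for infusion, so an attribution rule is needed for infusions inside the window. No treatment decision is affected.

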#### 9.7.1.2 Minimal Observed Treatment Period to Estimate ABR

For enrolled subjects that have met all inclusion and exclusion criteria, subjects who have at least 1 assessment [defined as having a minimum of 3-month (≥90 days) observational period on regimen] but do not complete the full study period of four years, the annualized bleeding rate will be estimated from the interval assessments.

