## 9.7.3.1 Primary Endpoint

The primary endpoint, the ABR of all types of bleeding episodes, will be calculated for each subject and described for each regimen (on-demand and prophylaxis).

Separate descriptive efficacy analyses of ABR will be provided for each of the following treatment regimens, assuming minimum observed period is satisfied (≥90 days):

- On-demand treatment
- Standard prophylaxis
  - ➤ continuous prophylaxis (≥46 weeks: long-term) 
  - intermittent prophylaxis (≥12 weeks-46 weeks)
  - episodic prophylaxis (<12 weeks)

  - > peri-ITI prophylaxis
- TGA-guided dosing for prophylaxis treatment
- TGA-guided dosing for on-demand treatment

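### The ABR rules start on-demand time at enrolment for everyone and do not limit the pre-prophylaxis bleed discard to the prophylaxis rate, so the on-demand ABR is wrong for subjects who change regimen

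*Protocol*

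**What the plan says.** Protocol Section 9.7.3.1 makes the ABR of all bleeds the primary endpoint; it "will be calculated for each subject and described for each regimen (on-demand and prophylaxis". Section 9.7.1.1 defines the rate as "total number of bleeding episodes÷observed treatment period in days", multiplied by 365.25, and then fixes three things about bleeds and time:

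- On-demand start: "The observation period for the on-demand regimen will commence on the day of enrollment".
- Prophylaxis start: "the period for the prophylaxis arm will commence at the first prophylactic infusion once enrolled".
- Bleeds left out: "Bleeding occurring prior to the first prophylactic infusion will not be included for the estimation of bleed rate".

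Section 9.7.1.2 sets the minimum for estimating a rate, "defined as having a minimum of 3-month (≥90 days) observational period on regimen".

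The Abstract (Study design) leaves the regimen to the attending physician in routine practice and gives a 4-year observation period per subject. Section 9.7.3.1 also lists prophylaxis categories much shorter than that, for example "intermittent prophylaxis (≥12 weeks-46 weeks". The Summary of Changes for Amendment 2 records that the primary-endpoint text no longer assumes mutually exclusive regimens.

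**The concern.** The rules in Section 9.7.1.1 work when each subject belongs to one arm throughout. In this cohort nothing ties a subject to one regimen, and two of the rules then go wrong.

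First, a subject who starts on prophylaxis and later goes on demand has an on-demand period that still begins at enrolment. The prophylaxis days fall inside it.

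Second, the discard of bleeds before the first prophylactic infusion refers to bleed rate in general. For a subject who starts on demand and later begins prophylaxis, those are the on-demand bleeds. Taken literally, they are removed and counted under neither regimen.

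At stake is the on-demand half of the primary description. The study has no control group and tests no hypothesis, so the ABRs by regimen are themselves the main result. With about 55 planned subjects, a few switchers could shift a regimen summary.

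**Working it through.** **Inputs**

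- Formula: ABR = bleeds ÷ days × 365.25 (Section 9.7.1.1). In years this is bleeds ÷ years.
- Follow-up: 4 years per subject (Abstract, Study design).
- Rates: 28.7 per year on demand and 7.9 on prophylaxis, the medians that Section 7.1 cites from a randomised parallel study. Using them as one subject's constant true rates is an assumption made for illustration.
- Switch time: an assumption, varied from 1 to 3 years.

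**Check on the cited rates.** 1 − 7.9/28.7 = 0.725, which matches the 72.5% reduction in Section 7.1. The protocol states no power or precision figure that could be reproduced for this endpoint.

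**Prophylaxis first, then on demand (2 + 2 years).** Bleeds: 2 × 7.9 = 15.8 on prophylaxis and 2 × 28.7 = 57.4 on demand.

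- On-demand period from enrolment, all bleeds counted: (15.8 + 57.4)/4 = 18.3.
- On-demand period from enrolment, only on-demand bleeds counted: 57.4/4 = 14.35, about 14.4.
- Own days and own bleeds: 57.4/2 = 28.7.

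With the switch at 1 year the two literal readings give (7.9 + 86.1)/4 = 23.5 and 86.1/4 = 21.5. With the switch at 3 years they give (23.7 + 28.7)/4 = 13.1 and 28.7/4 = 7.2.

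**On demand first, then prophylaxis (1 + 3 years).** Bleeds: 28.7 on demand and 3 × 7.9 = 23.7 on prophylaxis. The on-demand ABR is:

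- Period left open, discard not applied: (28.7 + 23.7)/4 = 13.1.
- Period left open, discard applied: 23.7/4 = 5.9.
- Period closed at the switch, discard applied: 0/1 = 0.
- Period closed at the switch, discard limited to the prophylaxis rate: 28.7/1 = 28.7.

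With the switch at 3 years, the first two readings give (86.1 + 7.9)/4 = 23.5 and 7.9/4 = 2.0. The prophylaxis ABR is 23.7/3 = 7.9 in every reading of the 1 + 3 case, because its numerator and denominator start together.

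**Pattern.** With these rates every literal reading lowers the on-demand ABR below 28.7. When each regimen has its own dated time and its own bleeds, the subject gets 28.7 and 7.9 at every switch time and in either order.

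**The case against.** The strongest reply is that Section 9.7.1.1 is shorthand that a statistical analysis plan would complete. The denominator is called an observed treatment period, and Section 9.7.1.2 speaks of time on regimen. The discard sentence stands next to the rule that starts the prophylaxis clock, so its natural purpose is to align bleeds and days for the prophylaxis rate. On that reading it is correct and needs only a clarifying phrase.

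Much of this stands, and it rules out a stronger inference. A reader might conclude that, because no end is given for prophylaxis, days and bleeds after stopping stay in the prophylaxis rate and inflate it several-fold. The documents do not support that. Sections 9.1.1, 9.3.1.1 and 9.7.3.2 rate prophylaxis at the end of each prophylaxis period, and Section 9.7.3.1 classifies it by duration, so prophylaxis time is meant to be bounded. A missing end date alone is ordinary analysis-plan detail.

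The same goes for three further inferences:

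- **Elective surgery.** The protocol says "The treatment period for emergency surgery will be excluded from the bleed rate calculation". A reader might infer that elective surgery is wrongly kept in. That contradicts nothing in the protocol and may be a deliberate choice in a routine-practice study.
- **Frequent switching.** Short prophylaxis categories do not prove long spells off prophylaxis, since Section 9.3.6 allows a subject to leave after successful ITI or disappearance of the inhibitor. The regimen changes mentioned in Section 7.1 may mean tailoring within prophylaxis.
- **Switchers bleed most.** This is conjecture.

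What the reply does not remove is the on-demand start. It is stated, not left open. For a subject on prophylaxis first, an analysis plan would have to contradict it, not add detail to it. The discard sentence also remains without a named rate.

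**Conclusion.** The point holds for the two stated rules: the fixed enrolment start of on-demand time, and the discard that is not limited to the prophylaxis rate. Applied as written, they give a wrong on-demand ABR for a subject who changes regimen. In the illustration the value is 18.3 or about 14.4 for two years of prophylaxis then two on demand, and 13.1, 5.9 or 0 for one year on demand then three on prophylaxis, against 28.7 in each case.

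These are sizes for one hypothetical subject. They rest on treating study medians as constant individual rates and on chosen switch times. The protocol does not give the number of switchers, so the effect on the regimen summaries cannot be stated, and subjects who stay on one regimen are essentially unaffected. Misallocation is what the written rules produce; it is not shown that the final analysis will follow them literally. The wording should be fixed because it bears on the primary endpoint and is cheap to correct. It does not undermine the study.

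**What to change.** Rewrite the time rules in Section 9.7.1.1 around dated regimen intervals for each subject:

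1. On-demand time starts at the later of enrolment or the end of a prophylaxis course. It stops at the next first prophylactic infusion or at study end.
2. Prophylaxis time runs from the first prophylactic infusion of a course to the end of that course, with the end derived from the infusion records by a stated rule.
3. Each bleed is assigned to the regimen in force at its onset.
4. Intervals are pooled into one ABR per subject per regimen. The text should say that the 90-day minimum applies to the pooled time, because a single course under 12 weeks (84 days) cannot reach it.
5. The sentence on bleeds before the first prophylactic infusion is limited to the prophylaxis rate.

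The cost is wording and some programming. Infusions and bleeds are already collected. The one real difficulty is the end of a course: home infusion data come partly from a voluntary diary (Section 9.4.2), so a rule is needed to separate a gap in recording from a stop in prophylaxis.

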#### 9.7.1.2 Minimal Observed Treatment Period to Estimate ABR

For enrolled subjects that have met all inclusion and exclusion criteria, subjects who have at least 1 assessment [defined as having a minimum of 3-month (≥90 days) observational period on regimen] but do not complete the full study period of four years, the annualized bleeding rate will be estimated from the interval assessments.

## 9.7.2 Handling of Missing, Unused, and Spurious Data

If a subject's weight is missing from any infusion record, the subject's last recorded weight will be used to calculate the weight-adjusted dose (U/kg).

In general, no additional techniques will be employed to adjust for missing data.

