# 9.1.1 Primary Endpoints

# Hemostatic and Preventative Efficacy

The primary objective to describe the hemostatic effectiveness of FEIBA-NF in haemophilia A or B patients with high responding inhibitors will be assessed as follows:

- For treatment of bleeding episodes in subjects on on-demand and for breakthrough bleeds in subjects on prophylaxis treatment
  - Annualized bleeding rate (ABR) and/or monthly bleeding rate (MBR), all bleeds
  - ➤ ABR or MBR, all joint bleeding events
  - > Total number of infusions of FEIBA NF required to control bleeds
  - > Total weight adjusted dose (U/kg) of FEIBA NF required to control bleeds
  - Total units infused (U) of FEIBA NF required to control bleeds
  - > Assessment of effectiveness:
    - Total number (%) of treated bleeds and their corresponding hemostatic efficacy ratings using an "excellent-to-poor" 4-point Likert scale by the subjects or caregiver for treatments given at home or by the investigator for treatments given in the hospital/clinic.
- For prevention of bleeding episodes:
  - Annualized bleeding rate (ABR) and/or monthly bleeding rate (MBR), all bleeds
  - > ABR or MBR, all joint bleeding events
  - > Assessment of effectiveness:
    - Total number (%) of bleeding episodes with corresponding hemostatic efficacy ratings with an "excellent-to-poor" 4-point scale by the subjects or care-giver at the end of each prophylaxis period (possibly rated within 24 hours from the end of the prophylactic treatment) or on an annual basis depending on which occurs first.
  - Total units infused (U), total weight adjusted dose (U/kg), and total number of infusions of FEIBA NF.

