#### 9.2.3.1 Inclusion Criteria

Subjects of any age who meet **ALL** of the following criteria are eligible for this study and who are willing and able to comply with the requirements of the protocol:

- Subject is a male congenital haemophilia A or B patient with high-responding inhibitor of any titer diagnosed before study entry
- Subject has been prescribed treatment with FEIBA NF as part of routine clinical practice, either on-demand, as prophylactic treatment or during ITI

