## 9.3.5.2 Physical Examination

Physical examination will be performed according to local routine at annual visits to the site. At screening, if an abnormal condition is detected, the condition will be described on the medical history CRF. At subsequent study visits, if a new abnormal or worsened abnormal pre-existing condition is detected, the condition will be described on the AE CRF. If the abnormal value was not deemed an AE because it was due to an error, due to a pre-existing disease (described in Section 11.2.6) not clinically significant, a symptom of a new/worsened condition already recorded as an AE, or due to another issue that will be specified, the investigator will record the justification on the source record.

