## 9.4.2 Subject Diary

It is considered standard practice for subjects with hemophilia to maintain a diary which captures treatments and disease related data. A subject diary will be provided to each subject at the screening visit and at annual interval visit(s), as needed, to help with the standardization of data collection method. Nevertheless, the completion of the diary is a voluntary effort by the individual subject or subject's legally authorized representative. A subject diary should allow to capture the following information:

- Infusion log for FEIBA NF
- Bleeding episodes
- Effectiveness assessment for treatment of each bleed
- Effectiveness assessment for prophylaxis therapy
- Acute pain associated with hemophilia, as measured with individual bleeding
  episodes, using the NRS (or Wong Baker Face Scale). VAS can also be used if
  routine practice at the centre. Acute pain will be assessed by the subject for each
  bleeding event and reported on the diary
- Chronic pain will be assessed using NRS on annual basis or more frequently according to routine practice at the site.
- Number of days lost from school or work due to bleeding episodes or their treatment
- Adverse events
- Concomitant medications / Non-drug therapies
- Duration of infusion of FEIBA NF

Diary data will be captured remotely by the subject entering them into a particular part of the electronic CRF (e-CRF). During the study, the investigator has access to the database holding the subject diary data. Upon retrieval of subject diaries at site closure, the site will receive the pdf files with the subject entries, including the audit trail.

All AEs regardless of causality and the number of bleed occurrences recorded in the subject diary during study participation period will be transcribed onto the CRF. For other types of data, such as global effectiveness and pain assessments, in the subject diary, every attempt will be made to collect all data as stated in this protocol. There will be no imputation on any endpoint in this study. Therefore, missing data will be labeled as such.

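### Filling a missing infusion weight with the last recorded weight overstates U/kg in growing children, by an amount the protocol does not let one determine

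*Protocol*

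**What the plan says.** Section 9.7.2 fixes the rule for any infusion record without a weight: "the subject's last recorded weight will be used to calculate the weight-adjusted dose (U/kg"). It then closes the subject: "In general, no additional techniques will be employed to adjust for missing data". Neither sentence mentions age or the time since the weight was taken.

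Eligibility under 9.2.3.1 opens with "Subjects of any age who meet" the criteria, and 9.1 follows each subject for 4 years. Section 9.1.1 lists "Total weight adjusted dose (U/kg) of FEIBA NF required to control bleeds" among the primary endpoints, and lists weight-adjusted dose again under prevention of bleeding. Section 9.7.3.2 summarises U/kg by regimen per bleed, per infusion, per week, per month, annualised and in total.

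On the source of weights the protocol says little. Section 9.3.5.2 states: "Physical examination will be performed according to local routine at annual visits to the site". It does not name weight. Section 9.2.6 expects a minimum of one site visit a year. Section 9.3.4 names body weight at infusion, but only for thrombin generation testing. Section 9.4.2, on the diary, says "There will be no imputation on any endpoint in this study".

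**The concern.** For adults of stable weight, carrying a weight forward is harmless. For children it is not neutral: they gain weight, so the carried value lies below the true weight on the infusion day and the computed U/kg is too high. The error runs in one direction, so enrolling more subjects does not average it out. The protocol wants to describe the regimens used in practice, and U/kg is the measure that makes doses comparable across body sizes. A rule that shifts it in one age group only is a poor choice when a better one can be programmed from the same recorded weights.

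There is also a wording point. Section 9.4.2 rules out imputation for every endpoint, while 9.7.2 imputes the denominator of a listed one.

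**Working it through.** The protocol gives no figure for this bias, so there is none to reproduce. The share of children, the share of infusion records without a weight, the growth rate and the time since the last weight are all absent and are treated below as assumptions.

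**Direction.** Computed U/kg divided by true U/kg equals true weight at infusion divided by carried weight. If the child has grown since the carried weight was taken, this ratio exceeds 1.

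**Size in affected children.** Take relative growth *g* per year, linear, and a gap of *T* years between weights. The overstatement at the end of the gap is *g* × *T*; averaged over the gap it is *g* × *T* / 2.

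| Assumed *g* | *T* = 1 year: end / average | *T* = 0.25 year: end / average |
|---|---|---|
| 0% (stable adult) | 0 / 0 | 0 / 0 |
| 5% | 5% / 2.5% | 1.2% / 0.6% |
| 10% | 10% / 5% | 2.5% / 1.25% |
| 15% | 15% / 7.5% | 3.8% / 1.9% |

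For scale only, take a true 85 U/kg, the target dose of an earlier trial cited in section 7.1. With a 1-year gap it would read on average 85 × 1.025 = 87.1, 85 × 1.05 = 89.2 or 85 × 1.075 = 91.4 U/kg at 5%, 10% or 15% growth.

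**Size in a pooled mean.** The shift is share of children × share of weights missing × *g* × *T* / 2. With *T* = 1 year, the smallest assumed combination gives 0.25 × 0.25 × 2.5% = 0.16%, and the largest gives 0.75 × 1.00 × 7.5% = 5.6%. The planned summaries in 9.7.3.2 are mostly medians with quartiles, so these figures show the order of size and do not predict the reported statistic.

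**Effect of interpolation.** Suppose true growth is exponential at *g* per year and weights are taken yearly. Carrying forward then gives a mean error of *g* / ln(1 + *g*) − 1, which is +2.5%, +4.9% and +7.3% at 5%, 10% and 15%. Linear interpolation between the two yearly weights leaves −0.02%, −0.08% and −0.16%.

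**Dependence on the reading of the rule.** The upward direction assumes that the weight carried is the latest one before the infusion. That is the natural reading, but 9.7.2 does not spell it out. If a programmer took the final weight of the 4-year record, the mean error would be (1 − (1 + *g*)^−4) / (4 ln(1 + *g*)) − 1, or about −9%, −17% and −23% at the same growth rates.

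**The case against.** The strongest reply is that the effect may be small and rare. Section 9.7.2 is worded conditionally, which implies that the infusion record has a place for weight and that an empty one is the exception. A reader might infer that filling will be the usual case for home infusions, because the diary list in 9.4.2 names an infusion log but no weight. The documents do not support that. The same list does not name units or lots either, yet 9.7.3.2 tabulates both, so it is not a list of data fields. A reader might also infer yearly weighing. One visit a year is a minimum, no weighing schedule is stated, and any infusion record that does carry a weight resets the carried value. This part of the objection stands: frequency and gap are unknown.

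Three further inferences also go too far.

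- U/kg is listed in 9.1.1, but 9.7.3.1 speaks of "The primary endpoint, the ABR of all types of bleeding episodes", and 9.7.3.2 places U/kg among the other primary criteria. ABR uses no weight.
- It is tempting to say that paediatric dosing will look higher than adult dosing. Doses are summarised by regimen, and no child-versus-adult comparison is planned.
- It is tempting to say that infusions will appear to exceed the 100 U/kg and 200 U/kg per day figures in 9.2.1. Those figures are product guidance, and no planned analysis counts infusions against them.

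On imputation, the sentence in 9.4.2 follows a passage on diary ratings, and 9.7.2 can be read as the single stated exception. The clash is a matter of wording. None of this changes the direction of the error in a growing child.

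**Conclusion.** The point holds in a limited form. For growing children with a missing infusion weight, the rule in 9.7.2 overstates U/kg whenever the carried weight predates the infusion. The average overstatement is about 2.5-7.5% with a 1-year gap and 0.6-1.9% with a 3-month gap, on assumed growth of 5-15% per year; it is zero in adults of stable weight. The effect on the whole cohort cannot be fixed from the protocol. The study is descriptive and its size has no statistical basis (9.5), so no test, error rate or sample size is affected. This is a bias in a descriptive dose summary that should be repaired because the repair is easy. The direction is certain under the natural reading of the rule; the size is not.

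**What to change.** Revise 9.7.2 as follows.

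- For subjects under 18, obtain a missing weight at the infusion date by linear interpolation between the nearest recorded weights before and after it.
- Use the most recent weight before the infusion only in adults and after a child's final measurement. State it in those terms, so that the undefined last recorded weight disappears.
- Report the number of filled weights by age group, so that readers can judge how much the rule matters.
- In 9.4.2, name this rule as an exception to the no-imputation statement.

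The cost is one programming rule applied to weights on record; no extra measurement is needed. Where a child has no later weight, the method falls back to carrying forward, so the gain depends on weights being recorded during follow-up. Paediatric U/kg in an interim report may be revised slightly when the next weight arrives, and the report should say so.
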